6 ANALYSIS METHODS

6.1 Study Subject Data

6.1.1 Subject Disposition

The number and percentage of subjects in each analysis population and final subject status (completed or withdrawn), including study discontinuation reasons, will be produced based on the number of randomized subjects. Data will be presented by study part and cohort.

Subjects contributing to each analysis population and final disposition status will be listed. Failed eligibility criteria for screen failures will also be included in a data listing. Alcohol breath test and drug screening results will be included in a data listing.

6.1.2 Protocol Deviations

Protocol deviations will be identified and classified as minor or major on the CRF before the database is locked. Major protocol deviations will be summarized by part, cohort, and deviation category using the SAF population.

A listing of all protocol deviations will be provided.

6.1.3 Demographic and Baseline Characteristics

Subject demographics and baseline characteristics will be summarized and listed. These will include age (as collected in the clinical database at the Screening visit), age category (18-<30, 30-<40, 40-<50, 50-55) sex (Male / Female), ethnicity (Hispanic or Latino / Not Hispanic or Latino), race (American Indian or Alaska Native / Asian / Black or African American / Native Hawaiian or Pacific Islander / White / Other / Not Reported), baseline height (cm), baseline weight (kg), BMI (kg/m²), and smoking status (Never Smoked / Current Smoker / Former Smoker). Subjects reporting multiple race categories will be summarized under the "Multiple" category. Data will be presented by study part and cohort for the SAF population.

A listing of demographics and baseline characteristics will be provided.

6.1.4 Medical History

General medical history (including clinically significant diseases and surgeries) will be summarized by Medical Dictionary for Medical Affairs (MedDRA) System Organ Class (SOC) and Preferred Term (PT) by study part and cohort for the SAF population. A subject will be counted only once at each level of reporting. SOC will be ordered in accordance with the international agreed upon sort order for SOC followed by descending order of overall PT incidence. The MedDRA version used for reporting will be described in the relevant table and listing footnotes.

General medical and surgical history will be presented in a by-subject data listing for the SAF population.

6.1.5 Prior and Concomitant Medication

The incidence of concomitant medication use will be summarized by WHO Drug Dictionary (WHODD) anatomic therapeutic chemical (ATC) Level 2 classification (i.e., therapeutic main group) and preferred name. The WHODD version used for reporting will be provided in the relevant table and listing footnotes.

A subject will be counted only once at each level of reporting. Prior medications are those which have been identified to have been discontinued prior to the treatment start date (e.g., taken exclusively during the pre-therapy period). Concomitant therapies are defined as all therapy

ongoing at the time of enrollment and all therapy other than study drug received during the study. Concomitant medication use will be summarized and presented by study part and cohort for the SAF population. Partial start/end dates will be imputed according to Appendix 1 for the determination of concomitance. Medications will be sorted by decreasing frequency of ATC classification based on overall subjects. Preferred drug names will be sorted in descending order by frequency within each ATC classification based on overall subjects.

All prior and concomitant medication data will be listed including the verbatim and preferred drug name and ATC Level 2.

6.1.6 Study Drug Exposure and Compliance

Study drug administration information recorded on the CRF will be presented in a data listing for the SAF population.

6.2 Efficacy

This study enrolls healthy volunteers; efficacy will not be evaluated.

6.3 Pharmacokinetics

6.3.1 Plasma Pharmacokinetic Parameters

The plasma PK parameters described in this section will be derived for KNX100 and metabolites (data permitting) based on the plasma concentration-time profiles as observed after the study drug administrations. Derivations will be based on the actual elapsed time (hours) since the study drug administration.

The pharmacokinetic concentrations will be processed using standard non-compartmental analytical approach to derive the required parameters. The software used for the analysis will be Phoenix™ WinNonlin® v8.3 (Pharsight Corporation, USA).

The PK parameters described in Table 4 will be derived provided that the required concentrations data are available. Concentrations below the limit of quantification (BLQ) will be treated as zero for descriptive statistics. Mean BLQ concentrations will be presented as BLQ, and the standard deviation (SD) and coefficient of variation (CV) will be reported as not applicable. Missing concentrations will be excluded from the calculations.

Table 4 Plasma PK Parameters

Where possible, the following PK parameters of KNX100 and any measurable metabolites will be determined.

SAD

Parameter (Unit)	Method
C _{max} (ng/mL)	Maximum plasma concentration obtained directly from the observed concentration versus time data
AUC _{0-∞} (h*ng/mL)	Area under the plasma concentration-time curve from time zero (pre-dose) extrapolated to infinity (units) calculated by linear trapezoidal rule and extrapolated to infinity by the addition of the last quantifiable concentration divided by the terminal rate constant: AUC _{0-last} + C _{last} /λ _z
AUC _{0-last} (h*ng/mL)	Area under the plasma concentration-time curve from time zero to the time of the last quantifiable concentration at time "t" (units), calculated by linear trapezoidal rule
AUC ₀₋₈ (h*ng/mL)	Area under the plasma concentration-time curve from time zero to 8 hours after dosing, calculated by linear trapezoidal rule
T _{max} (h)	Time to maximum plasma concentration obtained directly from the observed concentration versus time data
CL/F (L/h)	Plasma clearance estimated as dose divided by AUC _{0-∞}
V _z /F (L)	volume of distribution estimated by dividing the apparent clearance by λ _z
λ _z (h ⁻¹)	Apparent terminal elimination rate constant estimated by log-linear least-squared regression of the terminal part of the concentration-time curve profile
t _{1/2} (h)	Elimination half-life, calculated as ln(2)/λ _z .
Residual area	Percentage of AUC _{0-∞} due to extrapolation from the time of last non-zero concentration to infinity.
DN AUC	Dose-normalized AUC, calculated as AUC/ Dose where AUC is AUC ₀₋₈ and AUC _{0-last}
DN C _{max}	Dose-normalized C _{max} , calculated as C _{max} / Dose

MAD

Parameter (Unit)	Method
C _{max} (ng/mL)	Maximum plasma concentration obtained directly from the observed concentration versus time data, Day 1 and Day 7
AUC _{0-∞} (h*ng/mL)	Area under the plasma concentration-time curve from time zero (pre-dose) extrapolated to infinity (units) calculated by linear trapezoidal rule and extrapolated to infinity by the addition of the last quantifiable concentration divided by the terminal rate constant: AUC _{0-last} + C _{last} /λ _z . Day 7 only
AUC _{0-last} (h*ng/mL)	Area under the plasma concentration-time curve from time zero to the time of the last quantifiable concentration at time "t" (units), over the whole plasma profile on Days 1 and 7, calculated by linear trapezoidal rule. Cohorts 1, 2 and 3
AUC _{0-8h} (h*ng/mL)	Area under the plasma concentration-time curve from time zero to 8 hours after dosing, calculated by linear trapezoidal rule. Days 1 and 7, Cohorts 1, 2 and 3
AUC _{8-16h} (h*ng/mL)	Area under the plasma concentration-time curve from time 8 hours to 16 h after first dose, calculated by linear trapezoidal rule. Days 1 and 7, Cohort 3
T _{max} (h)	Time to maximum plasma concentration obtained directly from the observed concentration versus time data. Day 1 and Day 7
CL/F _{ss} (L/h)	Plasma clearance estimated as dose divided by AUC _{0-tau} . Day 7 only where data permits
V _z /F (L)	volume of distribution estimated by dividing the apparent clearance by λ _z . Day 7 only
λ _z (h ⁻¹)	Apparent terminal elimination rate constant estimated by log-linear least-squared regression of the terminal part of the concentration-time curve profile. Day 7 only
t _{1/2} (h)	Elimination half-life, calculated as ln(2)/λ _z . Day 7 only
Residual area	Percentage of AUC _{0-∞} due to extrapolation from the time of last non-zero concentration to infinity. Day 7 only
RA AUC	Accumulation Ratio for AUC, calculated as AUC _{Day 7} / AUC _{Day 1} , Cohorts 1, 2 and 3 (note the time interval over which the AUC will be determined will be dependent on the quantifiable data).

Parameter (Unit)	Method
RA Cmax	Accumulation Ratio for Cmax, calculated as Cmax Day 7 / Cmax Day 1
MR AUC	Metabolite to parent ratio for AUC, calculated as Ratio of [AUC (metabolite)/AUC (parent)] * [mw (parent)/mw (metabolite)] where AUC is AUC0-8
MR Cmax	Metabolite to parent ratio for Cmax, calculated as ratio of [Cmax (metabolite)/ Cmax (parent)] * [mw (parent)/mw (metabolite)] on Day 7 only

For non-compartmental analysis, λ_z will be the negative of the estimated slope of the linear regression of the log transformed concentration (natural logarithm) versus time profile in the terminal elimination phase.

At least three concentration points will be used in estimating λ_z . The time point where log-linear λ_z calculation begins (λ_z Lower), and the actual sampling time of the last quantifiable concentration used to estimate the λ_z (λ_z Upper) will be reported with the correlation coefficient from the linear regression (R2 adjusted) to calculate λ_z .

Rsq adjusted, the goodness of fit statistic for the terminal elimination phase, adjusted for the number of points used in the estimation of λ_z must be ≥ 0.8 .

If the λ_z cannot be measured (e.g.: fewer than 3 non-zero concentrations in the terminal elimination phase), then elimination related PK parameters (λ_z , λ_z Lower, λ_z Upper, AUC0- ∞ , Rsq adjusted, Residual area, T1/2, CL/F, and Vz/F) will not be reported for PK profiles. If Rsq adjusted < 0.8, then λ_z , and its related PK parameters (λ_z , λ_z Lower, λ_z Upper, AUC0- ∞ , Rsq adjusted, Residual area, T1/2, CL/F, and Vz/F) will be flagged in individual listings, and excluded from analyses.

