5.3.3. Part B Dosing

In Cohorts 1 and 2, study drug will be administered once daily for 7 days at approximately the same time each day \pm 30 minutes. In Cohort 3, study drug will be administered twice daily, approximately 8 hours (\pm 30 minutes) apart for 7 days. Doses will be administered:

- Morning (e.g., at 11:00 am) at approximately the same time (\pm 30 minutes) each day
- Afternoon/ Evening (e.g., at 7:00 pm) at approximately the same time (\pm 30 minutes) each day

The first dose of study drug will be administered together with a glass of tap water under a fasted state i.e., after an overnight fast of at least 10 hours. For MAD Cohort 3, the second dose of study drug will be administered together with a glass of tap water under a fasted state i.e., after fasting for at least 2 hours prior to dose administration. For all cohorts, no food is allowed for at least 2 hours after drug administration. Please refer to [Section 5.10.3](#) for information related to fluid and food restrictions both pre- and postdose.

[Table 4](#) provides the planned dose-escalation schedule for Part B (MAD). Up to 2 dose strengths ranging from as low as 10 mg and up to the clinical exposure cap will be selected based on the tolerability and pharmacokinetics of the previous dose.

Table 4 Planned Dose-Escalation Schedule (MAD Part B)

Cohort	Oral Daily Dose (mg/day) ¹		Total Number of Capsules/Day (Number - Strength) ¹	
	KNX100	Placebo	KNX100	Placebo ²
1	10 (Low)	0	2 capsules (2 × 5 mg)	2 capsules (2 × 0 mg)
2	30 (High)	0	2 capsules (1 × 5 mg, 1 × 25 mg)	2 capsules (2 × 0 mg)
3	30 (bid) ³	0	2 capsules (1 × 5 mg, 1 × 25 mg) (am) 2 capsules (1 × 5 mg, 1 × 25 mg) (pm)	2 capsules (2 × 0 mg) (am) 2 capsules (2 × 0 mg) (pm)

Abbreviations: am = morning; bid = twice daily; MAD = multiple ascending dose; pm = afternoon/evening

¹ Dose levels will be based on data from Part A and emerging PK data.

² An equivalent number of capsules will be administered to subjects receiving placebo.

³ Dose to be administered twice daily, 8 hours apart (refer also to [Section 5.3.3](#)).

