⁷ Vital signs will be measured with the subject to be seated or semi-supine after resting for at least 3 minutes. Measurements will include systolic and diastolic blood pressures, pulse rate, body temperature, respiratory rate, saturated oxygen and pulse oximetry which will be recorded via telemetry within 2 hours predose and at 2 hours postdose (± 15 minutes). Peak flow measurement will also be undertaken within 1 hour predose as well as at 1-, 2-, and 4-hours (± 15 minutes) postdose. The highest of 3 peak flow measurements, at each timepoint, shall be recorded. For MAD Cohort 3, vital signs, telemetry, and peak flow measurements will be recorded following each dose as per the schedule above.

⁸ Laboratory tests will be undertaken as depicted above. The Day 1 laboratory tests will be undertaken 1 hour post morning dose (± 15 minutes).

⁹ A serum pregnancy test will be undertaken at screening and End of Study visit. A urine pregnancy test will be conducted in women of child-bearing potential on admission (Day -3).

¹⁰ Drug abuse screening and alcohol breath test will be conducted at admission (Day -3).

¹¹ Subjects in Cohorts 1 and 2 of the MAD study phase will be dosed daily for 7 days at approximately the same time each day. Each subject will receive study drug based on randomization (placebo or KNX100), after a 10 hour fast. Subjects will remain fasted until 2 hours (±15 minutes) post study drug administration.

Subjects in Cohort 3 of the MAD study phase will be dosed twice daily (b.i.d) with doses administered approximately 8 hours (\pm 30 minutes) apart. The first dose will be administered following a 10 hour overnight fast, and subjects will remain fasted until 2hours (\pm 15 minutes) post study drug administration. Subjects will be required to fast 2 hours (\pm 15 minutes) prior to administration of the second dose of study drug and will remain fasted until 2hours (\pm 15 minutes) post study drug administration.

¹²Please refer to [Appendix 3](#) for information related to PK assessments and sampling times. The timing and number of PK samples may be altered depending on emerging data and safety profile. Please note, Day 4 predose sample is not required for Cohort 3.

¹³ Plasma samples for biomarker analyses will be collected predose (Day -1), and 1 hour post morning dose (\pm 15 minutes) on Days 1, 2, 3, 7 and at the ET/EOS visit.

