⁴ A 1-hour (± 15 minutes) EEG will be collected during Part A (SAD) at screening under sleep deprived conditions (after only 4 hours of sleep) and 24 hour ambulatory EEGs will be collected from at least 30 minutes (± 10 minutes) predose until 24 hours (± 1 hour) postdose (Day 1). During Part B (MAD), a 1-hour (± 15 minutes) EEG will be collected at screening under sleep deprived conditions (after only 4 hours of sleep) and a 24-hour ambulatory EEG will be collected from at least 30 minutes (± 10 minutes) predose (Day 1) until at least 2 hours post morning dose (Day 2). This will incorporate both pre- and post-Day 2 dosing. On Days 3, 4, 5, and 6, a 2-hour (± 10 minutes) postdose EEG will be collected commencing at least 30 minutes predose until at least 120 minutes post morning dose. On Day 7, a 24-hour ambulatory EEG will be collected from at least 30 minutes (± 10 minutes) predose until 24 hours (± 1 hour) post morning dose (Day 8). Additional EEGs may be performed as deemed necessary and as data emerges from study cohorts.

⁵ During Part B (MAD Cohort3), PK samples will be taken at predose and 30 minutes (± 2 minutes), 1-hour (± 5 minutes), 2-, 4-, 8- (predose for 2nd dose), 8.5-, 9-, 10-, 12- and 16- hours (± 15 minutes) postdose (Days 1 and 7 only). Note that the 8.5-, 9-, 10-, 12 and 16-hour timepoints represent 0.5-, 1-, 2-, 4-, and 8 hours *after* the 2nd dose).

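### In MAD Cohort 3 the SAP cuts AUC0-8h and AUC8-16h at 8 h after the first dose, so a second dose given before 8.0 h has part of its area credited to the first interval

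*SAP*

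**What the plan says.** **SAP 6.3.1, Table 4 (MAD).** Cohort 3 has two partial areas.
- AUC0-8h, shared with Cohorts 1 and 2: "Area under the plasma concentration-time curve from time zero to 8 hours after dosing, calculated by linear trapezoidal rule. Days 1 and 7".
- AUC8-16h, for Cohort 3 only: "Area under the plasma concentration-time curve from time 8 hours to 16 h after first dose, calculated by linear trapezoidal rule".

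On the time basis, the same section says: "Derivations will be based on the actual elapsed time (hours) since the study drug administration". It has no rule for restarting the clock, or moving the cut, at the second dose. In the metabolite-to-parent AUC ratio (MR AUC) the area is fixed: "where AUC is AUC0-8". For the accumulation ratio (RA AUC) the interval is left open, to depend on the quantifiable data. CL/Fss uses AUC0-tau, and Table 4 does not say what tau is for Cohort 3.

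**Protocol 5.3.3.** "In Cohort 3, study drug will be administered twice daily, approximately 8 hours" apart, with a tolerance of 30 minutes either way. Appendix 2, footnote 11, repeats this. Dose 2 may therefore fall anywhere from 7.5 to 8.5 h after dose 1.

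**Protocol Appendix 3, footnote 5.** The later Cohort 3 samples are listed as "8- (predose for 2nd dose), 8.5-, 9-, 10-, 12- and 16- hours (± 15 minutes) postdose (Days 1 and 7 only". The footnote adds that the samples from 8.5 to 16 h stand for 0.5 to 8 h after the second dose.

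**The concern.** The samples follow dose 2, while the cut between the two areas follows dose 1. The two agree only when dose 2 is given at exactly 8.0 h.

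If dose 2 is early, the first rise after it lies before the cut. That area is counted in AUC0-8h and is missing from AUC8-16h. If dose 2 is late, only the low tail of dose 1 changes sides, so early and late doses do not cancel.

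AUC8-16h exists only for Cohort 3 and isolates exposure after the second dose, and twice-daily PK is a listed secondary objective (Protocol 2.2). A reader will naturally compare the two areas, because dose 1 follows a fast of at least 10 hours and dose 2 a fast of at least 2 hours. A difference produced by the clock could be taken for lower exposure after the second dose. With six active subjects in the cohort, one or two early doses can move the summary.

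**Working it through.** **Figures from Protocol 3.2.1.** CL/F is 356,000 mL/h, and about 20 mg is estimated to give a Cmax of about 46 ng/mL. As a check on CL/F, 356,000 × 23.3 = 8,294,800 ng, or 8.3 mg, which is the protocol's own figure. The plan states no figure for the error examined here.

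**Shape of the curve.** AUC at 20 mg = 20,000,000 / 356,000 = 56.2 h·ng/mL. AUC/Cmax = 56.2 / 46 = 1.22 h.

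**Assumptions (not in the documents).** One compartment, first-order absorption, no lag, the same profile after each dose, and r = ka/ke between 1.5 and 20. In this model Cmax/AUC = ke · r^(−1/(r−1)), so ke = r^(1/(r−1)) / 1.2213. This gives half-lives of 0.38 to 0.72 h. The dose is set to the planned 30 mg (Protocol Table 4), so one dose has AUC = 30,000,000 / 356,000 = 84.3 h·ng/mL. The dose cancels in the percentages.

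**Area moved.** Let dose 2 be e hours early (e up to 0.5), and let C be the concentration 0.5 h after it. In this model the level just before dose 2 is close to zero. The linear rule joins the pre-dose sample to the 0.5 h sample by a straight line, so the height at the 8.0 h cut is 2eC. Area moved = ½ · e · 2eC = e²C.

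**Example, r = 2.** ke = 2 / 1.2213 = 1.64 per h and C = 68.0 ng/mL. The linear area from dose 1 to dose 2 is 82.6 h·ng/mL.
- Dose 2 at 7.5 h: 0.25 × 68.0 = 17.0, and 17.0 / 82.6 = 20.6%.
- Dose 2 at 7.75 h: 0.0625 × 68.0 = 4.25, and 4.25 / 82.6 = 5.1%.
- Mean, uniform over 7.5-8.5 h: (0.5³/3) × 68.0 / 1.0 = 2.83, and 2.83 / 82.6 = 3.4%.
- Mean, uniform over 7.75-8.5 h: (0.25³/3) × 68.0 / 0.75 = 0.47, and 0.47 / 82.6 = 0.57%.

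**Across the range: error in AUC0-8h against a cut at dose 2.**

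| ka/ke | C at 0.5 h (ng/mL) | Dose 2 at 7.5 h | Dose 2 at 7.75 h | Mean, 7.5-8.5 h | Mean, 7.75-8.5 h |
|---|---|---|---|---|---|
| 1.5 | 68.4 | +20.6% | +5.1% | +3.4% | +0.57% |
| 2 | 68.0 | +20.6% | +5.1% | +3.4% | +0.57% |
| 5 | 63.9 | +20.1% | +5.0% | +3.3% | +0.55% |
| 20 | 52.7 | +17.7% | +4.4% | +2.9% | +0.47% |

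AUC8-16h falls by nearly the same percentage in each early case. A dose at 8.25 or 8.5 h changes either area by less than 0.1%. The ratio of AUC8-16h to AUC0-8h, which should be about 1 here, becomes 0.66-0.71 for a dose at 7.5 h and 0.90-0.92 at 7.75 h.

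**Wider kinetics.** With Tmax 0.25-1 h and half-life 0.5-3 h, not tied to the protocol's Cmax, a dose at 7.5 h raises AUC0-8h by about 7% to 23% and lowers AUC8-16h by about 4% to 23%. A dose at 7.75 h raises AUC0-8h by about 2% to 6%. A late dose changes either area by at most about 2.3%, so even slow elimination gives only a partial offset.

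**The two windows.** The pre-dose-2 sample is due at 8 h ± 15 min, so from 7.75 to 8.25 h. If it is in window and precedes the dose, dose 2 cannot be earlier than 7.75 h. A dose at 7.5 h satisfies the dosing window but leaves no room for an in-window pre-dose sample, unless the sample window is read relative to dose 2.

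**The case against.** The strongest reply is that the intent is plain. Appendix 3 treats the 8 h sample as the pre-dose sample for dose 2 and the later ones as times after dose 2. A pharmacokineticist could use that sample as the boundary, and the problem would vanish. This is a fair account of what may happen, but it is not what the SAP says: its text combines a count from the first dose with actual elapsed time.

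The second reply is that the large figures need a dose at 7.5 h, which conflicts with the 15-minute sampling window. This stands. If that window holds, the worst case is about 5% and the mean about 0.5%.

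The third reply is that the kinetics are assumed. This also stands. The documents give no human Tmax or half-life, the 20 mg and 46 ng/mL pairing is a hedged estimate, and the shorter fast before dose 2 may change its profile.

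The fourth reply is that the knock-on effects are conditional. RA AUC may be based on AUC0-last, which the cut does not touch. If it uses AUC0-8h, it shifts only when dose-2 timing differs between Day 1 and Day 7, and nothing suggests a systematic difference. For scale, dose 2 on time on Day 1 and at 7.75 h on Day 7 would give a ratio of about 1.04-1.05 with no accumulation.

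A reader might also infer that about a third of a dose's area moves, with a mean error of 6-8%. Under the same model 31-35% of the true area does fall in the first 30 minutes, and 6-8% is the mean for true area over 7.5-8.5 h. But the SAP reports linear-trapezoid areas, for which the figures are about 18-21% and 3%.

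**Conclusion.** The point holds in a limited form. Followed as written, the SAP puts part of an early second dose into AUC0-8h and takes it out of AUC8-16h. This is a stated rule that gives the wrong value, not merely a missing detail.

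Under the assumed one-compartment model the error is about 4-5% in each area for a dose at 7.75 h. It is about 18-21% at 7.5 h, which requires an out-of-window pre-dose sample or a sample window read relative to dose 2. The mean error in AUC0-8h under uniform dose times is about 3% or about 0.5%, depending on which earliest dose time applies. A subject-day with dose 2 at or after 8.0 h is essentially unaffected under this model.

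MR AUC may be affected because it is tied to AUC0-8, and parent and metabolite need not rise equally fast after dose 2. RA AUC and CL/Fss are affected only if they use the 0-8 h interval.

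A reader might infer that the cohort's overall exposure, or the safety limit, is distorted. The documents do not support that. Whole-profile AUC0-last and Cmax do not depend on the cut, and the exposure cap in Protocol 6.20.1 is stated on those two. The study is descriptive, so no test is at stake. The correction is worth making because it is cheap and removes an avoidable error in small-sample summaries.

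**What to change.** In SAP Table 4 (MAD), define the Cohort 3 partial areas by the actual time of the second dose:
- first interval: from dose 1 to dose 2, with the pre-dose-2 sample as the boundary concentration;
- second interval: from dose 2 to the sample taken 8 h after it.

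Use these intervals on Days 1 and 7 for AUC, RA AUC and MR AUC. With this cut no second-dose area falls in the first interval, whatever the timing within 7.5-8.5 h.

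Separately, the 15-minute window for the pre-dose-2 sample (Appendix 3) and the 30-minute window for the second dose (Protocol 5.3.3 and Appendix 2) must be reconciled.

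The SAP change is about two lines. It uses samples already planned and the recorded dose times, and needs no new data.
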